## Objectives

This prospective randomised trial aims to test if Virtual Reality (VR) simulation helps medical students who have no surgical experience acquire basic surgical skills in total hip arthroplasty (THA) by performing two difficult THA steps: the acetabular cup and femoral stem implantation in a specific position. This study hypothesised that VR training could help young doctors orient themselves in space and perform more accurate cup implantation in 60° inclination and femoral stem in 20° anteversion than a control group that had only video teaching from an expert. The primary outcome will be the a. the difference in the mean implanted cup inclination and femoral stem anteversion between the VR and control group b. the mean difference between the asked predefined and the actual implanted cup inclination or cup version between the VR and control groups. Secondary outcomes will be other differences in completing the task between groups a. the time needed to complete the task and b. the times asking for assistance c. the number of mistakes.

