#### Pretest

Immediately after enrollment, medical students were asked to complete a multiple-choice pretest to quantify their baseline medical and procedural knowledge of hip arthritis and THA. All participants were unaware and unable to prepare for the pretest assessment, which allows the test scores to be considered an accurate measure of baseline knowledge.

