#### Randomisation

All participants were then randomised in the VR or control group for cup and stem training and implantation by a computerised random number generator. In detail, each participant was randomised in the VR group for the cup or the stem implantation but in the control group for the other part of the THA. So, participants enrolled on the VR group for cup training were the control group for the femoral stem training and vice versa. In this way, each participant was asked to do one implantation following VR training and the other without VR training. Participants were privately notified of their randomisation assignment and asked not to disclose their designated cohort with any other study participant or research personnel. Only a research team member

knew of the cohort assignments during this study. This study personnel did not participate in the evaluation and analysis of data.

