#### Power Analysis

After reviewing eight recent RCT studies on virtual reality simulation training, it was found that each study had an average of 14 to 28 participants and an effect size of 0.80 to 0.90. Previous studies have utilised specific scores to evaluate the impact of trauma or arthroplasty simulator training on actual performance in real-world scenarios. These evaluations were different from our measurements. To assess the necessary sample size for our study, we based on the first ten measurements of cup angle implantation from our medical students; the mean cup angle was 50.40 with a standard deviation of 18°. To detect a difference of 20 degrees of implantation

between two groups with a standard deviation of 18 degrees and with a two-sided alpha of 0.05 and power of 80%, at least 26 students were required in its group.

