**Figure 1, Study Design**

### **Statistical Analysis Plan (SAP)**

The primary outcome was the mean implanted cup inclination and femoral stem anteversion difference between the VR and control groups. Other outcomes considered between groups included: a) the duration required to complete the task, b) the frequency of requesting assistance, and c) the number of errors made.

We used standard statistical methods to gather descriptive statistics. We conducted the Kolmogorov-Smirnov and Shapiro-Wilk tests to check whether the data followed a normal distribution. Our statistical tests were two-tailed, and we set the alpha level at 0.05. For continuous variables that were normally distributed, we used the two-sided independent sample t-test, while for those that weren't normally distributed, we used the Mann-Whitney U-test. We compared categorical data using the chi-square test. To determine if using VR had an impact on a student's task performance, a paired t-test was conducted to compare their outcomes with and without VR. We performed all statistical analyses using SPSS software (IBM, version 27.0).

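### Normality tests can send the primary difference in means to a Mann-Whitney U-test, which does not test or estimate that difference

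*Combined protocol and SAP*

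**What the plan says.** The SAP states: "The primary outcome was the mean implanted cup inclination and femoral stem anteversion difference between the VR and control groups". Part (a) of the primary outcome in the Objectives is also a difference in means. Part (b) is "the mean difference between the asked predefined and the actual implanted cup inclination or cup version between the VR and control groups", without saying whether the deviation is signed or absolute. The Power Analysis sizes the trial on a difference of 20° between two groups with SD 18°.

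On the choice of test, the SAP says: "We conducted the Kolmogorov-Smirnov and Shapiro-Wilk tests to check whether the data followed a normal distribution". Normally distributed continuous variables go to the independent-samples t-test, "while for those that weren't normally distributed, we used the Mann-Whitney U-test". The primary angles are not exempted. The SAP gives no cut-off for the normality check, no rule for when the two checks disagree, and no confidence interval or effect estimate on either branch.

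**The concern.** The primary outcome is a property of means, but the test may not be. Mann-Whitney asks whether a value from one group tends to exceed a value from the other. That amounts to a shift in means only when the two distributions have the same shape. Otherwise it can reject although the means are equal.

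At stake is which question the primary p-value answers. That would be settled by a preliminary check on the trial's own data, and by whichever normality test the analyst lets govern. On the Mann-Whitney branch the p-value does not belong to the quantity named as primary, even if group means still appear among the descriptive statistics. Unequal shapes are not far-fetched: the hypothesis is that VR makes implantation more accurate, which could change the distribution of angles as well as its centre.

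**Working it through.** **Inputs from the documents.** Mean cup angle 50.4° and SD 18° (Power Analysis: "we based on the first ten measurements of cup angle implantation from our medical students"); 101 students enrolled (Recruitment); two-sided alpha 0.05 (SAP); cup target 60° (Objectives).

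**Assumptions.** A 50/51 split, since the ratio is not stated. Skewed angles drawn from a shifted gamma distribution, whose skewness is 2/√shape: shapes 4, 2 and 1 give 1.0, 1.4 and 2.0. SD 9° or 6° where VR is taken to narrow the spread. The gate is Shapiro-Wilk at 0.05 in each group. Kolmogorov-Smirnov is taken with the Lilliefors correction.

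**The plan's own figure.** The sample size is for a mean difference: 2 × (18 × (1.960 + 0.842) / 20)² = 12.7, so 13 per group (14 by the exact t-test). The stated 26 per group is not reproduced; 26 matches the total, 2 × 13. This is a separate matter. With 50/51 the standard error is 18 × √(1/50 + 1/51) = 3.58° and power for 20° is 99.98%, so power is not the issue here.

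**How often the gate opens.** With both groups normal at SD 18°, 9.4% of trials go to Mann-Whitney. With a normal VR group at SD 9° and a control group with skewness 1.4 at SD 18°, 96% do.

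**Rejection rates with both means at 50.4°.**

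| Scenario | Gated plan | Test on means |
|---|---|---|
| One group normal, the other with skewness 1.0 / 1.4 / 2.0, both SD 18° | 6.8% / 8.4% / 10.1% | 4.8% / 5.2% / 4.9% |
| VR normal SD 9°, control skewness 1.4, SD 18° | 21.1% | 5.3% |
| Both groups skewness 1.4, SD 9° against 18° | 20.5% | 5.4%* |
| Both normal, SD 9° or 6° against 18° | 5.2% to 5.3% | about 5% |
| Same skewed distribution in both (skewness 1.4, SD 18°) | 4.8% | 5.0% |

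The last column is Welch's test, except * which is the equal-variance t-test. Rows 2, 3 and 5 of the gated column rest on 4,000 trials each. The simulation error there is about √(0.05 × 0.95 / 4000) = 0.3 percentage points at 5%, and √(0.21 × 0.79 / 4000) = 0.6 points at 21%.

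In row 2 the true mean difference is 0°, yet the shift that goes with the rank test (Hodges-Lehmann, VR minus control) averages about −2.9°. The two analyses are estimating different things.

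**Disagreement between the two normality tests.** In a skewed group of 51, Shapiro-Wilk and Kolmogorov-Smirnov reach opposite conclusions in 33.6%, 25.7% and 4.3% of trials at skewness 1.0, 1.4 and 2.0.

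**Part (b) of the primary outcome.** Signed deviation gives the same group comparison as the raw angle: (mean VR − 60) − (mean control − 60) = mean VR − mean control. Absolute deviation does not. Even if the cup angle is normal (50.4°, SD 18°), its absolute distance from 60° fails Shapiro-Wilk in 91.5% of groups of 50 and Kolmogorov-Smirnov in 53.4%, and the two disagree in 38.4%. On that reading the missing rule would matter in over a third of groups.

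**The case against.** Choosing between these two tests by a normality check is common practice, and several points in its defence stand.

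- A reader might infer that the plan inflates false positives when VR does nothing. It does not: with one common distribution in both groups the gated plan rejects in about 5% of trials. The excess arises only when VR really changes the distribution.
- A reader might infer that any narrowing of spread under VR breaks the plan. With normal data it does not. It would be equally wrong to say that the groups must differ in skewness: with the same skewness in both and only the SD different, rejection is 20.5%.
- Nothing in the documents shows that the raw angles are skewed, so the 7% to 21% is conditional.
- A comparison of mean raw angles cannot see an improvement in accuracy that leaves the mean unchanged. This is a fair limit on a fix confined to the raw angle, and is why deviation from target must be covered too.
- With about 50 per group the t-test is robust to moderate skewness. That is an argument for dropping the gate.

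A reader might also object that the pretest score is unused. It was taken before allocation, so the unadjusted comparison is unbiased. The documents give no correlation with the implanted angle, and the gain is small at plausible values: at a correlation of 0.2 the standard error falls from 3.58° to 3.53°. Adjustment is at most an optional sensitivity analysis and is no part of this point.

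**Conclusion.** The concern holds in a limited form. The SAP's rule can replace the test of its stated primary quantity with a test of something else, without an interval and without a rule for conflicting normality tests. That follows from the text.

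The size depends on assumptions. With equal means, 50/51 students and some skewness, the gated plan rejects in about 7% to 10% of trials at equal SDs and about 21% with SDs of 9° and 18°, while Welch's test stays near 5%. Without skewness, or with no VR effect at all, there is little or no distortion.

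The documents do not show that Mann-Whitney was in fact used for the primary angles, or that any conclusion of the trial is wrong, and neither should be inferred. This is a worthwhile, inexpensive correction, not a threat to the trial's validity.

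**What to change.** For cup inclination and for stem anteversion, make the primary analysis the VR-minus-control mean difference with a 95% confidence interval, by Welch's method or a linear model with heteroscedasticity-robust standard errors, whatever the normality tests show. Report Mann-Whitney as a sensitivity analysis.

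Analyse deviation from target, part (b) of the primary outcome in the Objectives, in the same way, and state whether it is signed or absolute. Absolute deviation is the version that addresses the accuracy hypothesis; signed deviation repeats the raw-angle comparison.

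State whether outcomes by group were known when this was settled. The SAP is written in the past tense ("We performed all statistical analyses using SPSS software"), which suggests that they may have been, though the documents do not say. If they were known, disclose the change and report the analysis by the existing rule beside the new one.

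The cost is a few sentences in the SAP, with no new data and no change in sample size. If results were already known, there is the further cost of disclosing a post hoc change to the primary analysis.

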#### VR training

As mentioned, each participant was randomised and did one implantation, either the acetabular cup or the femoral stem, following VR training and the other (stem or cup) without VR training, respectively. This method allowed us to evaluate and compare the performance of participants who received VR training versus those who did not within the same implantation. It also enables us to assess individual participants' performance in both scenarios (stem or cup), with and without VR training.

Before the VR-THA training, participants were asked to complete a survey evaluating their previous VR technology experience. All VR group participants were then asked to complete three consecutive VR sessions using the VR system (ORama VR, Geneva, Switzerland), performing cup or stem implantation based on their group.

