#### Saw bone simulation

After completing VR training, all participants were asked to implant the cup at a 60° inclination in sawbones and the femoral stem at 20° of anteversion. As mentioned, they performed one implantation following VR training and the other without VR training.

[figure not shown]
The sawbones had been reamed and prepared appropriately to accommodate the metal prostheses from the students steadily. The students did not perform any reaming to the sawbones. The same saw bone was used for several implantations but was replaced with a new one when it could no longer handle the implant properly. The cup inclination and stem version were evaluated using specific goniometers and assessment of photographs taken during implantation. During implantation in sawbones, a study assistant was present and was instructed to intervene only if the study participants requested assistance or could not progress through the task.

Upon completion of the VR-THAs, participants completed a survey focused on their interest in using VR simulations for surgical skills training and assessing potential negative consequences.

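### The within-student paired t-test always sets a cup against a stem and has no task term, so it loses precision and is biased when the realised arms are unequal

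*Combined protocol and SAP*

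**What the plan says.** The Randomisation section states that "each participant was randomised in the VR group for the cup or the stem implantation but in the control group for the other part". Allocation was "for cup and stem training and implantation by a computerised random number generator"; no ratio, blocking or realised arm sizes are given, and Recruitment reports 101 students. The Saw bone simulation section asks students to "implant the cup at a 60° inclination in sawbones and the femoral stem at 20° of anteversion".

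The VR training section gives the design two uses. One is to "compare the performance of participants who received VR training versus those who did not within the same implantation". The other is to assess each student's "performance in both scenarios (stem or cup), with and without VR training". For the second use the SAP says only that "a paired t-test was conducted to compare their outcomes with and without VR". It does not say which outcome is paired or whether the two arms are pooled, and it names no task or arm term.

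**The concern.** No student performs the same component both with and without VR. The VR-minus-no-VR difference is cup minus stem for students given VR on the cup, and stem minus cup for the others. If the two tasks differ on the outcome for reasons unrelated to VR, that gap is added in one arm and subtracted in the other.

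Two consequences follow when the arms are pooled. The gap inflates the spread of the differences, so the interval is wider than the data warrant. If the arms are unequal, part of the gap also remains in the estimated VR effect. If the test were instead run within one arm, which the plan does not state, VR and task could not be separated at all.

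This is the only within-student test of VR in the plan. A null result could reflect task noise and a positive one arm imbalance, and a reader could not tell.

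**Working it through.** **Plan's own figure.** The documents give no sample size or power for the paired test. The Power Analysis figure of 26 concerns two independent groups (20° difference, SD 18°, two-sided 0.05, 80% power). Those inputs give 13 per group, 26 in total. That is a separate matter.

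**Inputs from the documents.** N = 101 (Recruitment); targets 60° and 20° (Saw bone simulation); "the mean cup angle was 50.40 with a standard deviation of 18" degrees (Power Analysis).

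**Assumptions.** Stem SD is also 18°, within-student correlation ρ = 0, data are normal, and VR has the same effect on both tasks, τ = 60 − 50.4 = 9.6°.

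**Model.** Let g be the cup-minus-stem gap under the same training, and D the VR-minus-no-VR difference for a student. D has mean τ + g in the cup-VR arm (n₁) and τ − g in the stem-VR arm (n₂). Hence:

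- Paired estimate: τ + g(n₁ − n₂)/N.
- SD of D with near-equal arms: √(2·18²(1 − ρ) + g²) = √(648 + g²) at ρ = 0.
- 95% half-width: 1.984 × SD/√101.
- Task-adjusted estimate (mean of the two arm means of D): τ at any split, with SE √648/√101 = 2.53° and half-width 5.0° at 51/50.

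**Near-equal arms.** On raw angles, g = 50.4 − 20 = 30.4° (pilot cup mean against stem target) or 60 − 20 = 40° (the two targets). On other outcomes g is unknown. Power and type I error are simulated, 20,000 runs per cell, with the larger arm at 51/50 being cup-VR.

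| Gap g | SD of D | Half-width | Paired power, 51/50 | Paired type I error, 51/50 | Paired power, simple randomisation |
|---|---|---|---|---|---|
| 0° | 25.5° | 5.0° | 96% | 4.9% | 96% |
| 10° | 27.3° | 5.4° | 95% | 3.6% | 94% |
| 18° | 31.2° | 6.2° | 92% | 1.6% | 87% |
| 30.4° | 39.7° | 7.8° | 79% | 0.2% | 67% |
| 40° | 47.4° | 9.4° | 59% | <0.1% | 53% |

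The task-adjusted test holds 96% power and about 5% type I error in every row. A hand check of the last row: at 51/50 the estimate centres on 9.6 + 40/101 = 10.0° with true SE 2.53°, and must exceed 9.4°. (10.0 − 9.4)/2.53 = 0.24, which gives about 59%.

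Averaged over simple randomisation, paired type I error is 4.9–5.1%. At the plan's 20° difference, paired power is about 100% at 51/50, and 99% at g = 40° under simple randomisation.

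**Unequal arms.** At 60/41 with no VR effect, the bias is g × 19/101.

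| Gap g | Bias | False positives |
|---|---|---|
| 10° | 1.9° | 9% |
| 18° | 3.4° | 14–15% |
| 30.4° | 5.7° | 21% |
| 40° | 7.5° | 25% |

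Under simple 1:1 randomisation, a split of 55/46 or worse has probability 0.43 and 60/41 or worse 0.07.

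**Free of the angle scale.** For any outcome with a gap of 1 SD, ρ = 0.3 and an effect of 0.4 SD, task-adjusted power is 92%. Paired power is 81% at 51/50 and 73% under simple randomisation.

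**The case against.** The strongest reply is that the large figures come from pairing raw cup inclination with raw stem anteversion, which the plan never says it does. The Objectives already name a target-referenced outcome, "the mean difference between the asked predefined and the actual implanted cup inclination or cup version", although that wording mentions only the cup. On absolute deviation, the pilot figures under normality give a cup mean of about 16.4° and SD of about 12°. An unbiased stem with SD 18° has a mean deviation near 14.4°, so the gap is 2° and the 60/41 bias 0.4°. With half that stem SD, the gap is about 9°, the SD of the differences rises about 21%, and the bias is 1.7° at 60/41 and 0.1° at 51/50. The documents contain no stem data, so these too are assumptions.

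This stands as to size: 30.4° and 40° are a worst case for raw angles, and 18° would require stems to be placed much worse than cups if deviation is used. It does not remove the defect, because the plan leaves the paired outcome open and gives nothing to show that cup and stem match on time, assistance or errors.

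Three further points are correct. The bias depends on the realised split and averages to zero under simple randomisation. The 9.6° effect common to both tasks is an assumption; if VR moved stems and cups in opposite directions, the pooled raw-angle effect would shrink under either analysis. The paired test is not the primary analysis. A last point, that assistance requests and errors are likely to be skewed counts, bears on the remedy and is met there.

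**Conclusion.** The concern holds. Every within-student pair is a cup against a stem, and no task term is planned. With near-equal arms the test is conservative and imprecise. With unequal arms it is biased, given the split, by gap × (n₁ − n₂)/101. Averaged over simple randomisation it is inefficient rather than invalid.

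The size depends on a gap that the documents fix only for raw angles. Harm is small at 5–10°, moderate at 1 SD (92% to 81% power in the example above) and large only on raw angles. Power is hardly affected at a true difference of 20°. The figures rest on SD 18° for both tasks, zero correlation unless stated otherwise, and an equal VR effect on both tasks. The comparison of VR with control within one component is untouched. The change is still worth making, because when the gap is zero the adjusted test gives up essentially nothing (96% power either way).

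**What to change.** Replace the paired t-test with a task-adjusted analysis pooled over both arms: a linear mixed model with fixed effects for task (cup or stem) and VR (yes or no) and a random student effect. Equivalently, compute each student's cup-minus-stem difference, compare it between the two randomised arms with a two-sample t-test, and halve the arm difference. Either estimates the average of the cup and stem VR effects.

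State which outcomes are analysed this way. For the angle, use the absolute deviation from the requested value, since different targets make raw angles non-comparable. Where the differences are clearly non-normal, as is likely for assistance requests and errors, the Mann-Whitney test already named in the SAP can compare the cup-minus-stem differences between arms. Report the realised arm sizes, and keep the same-component group comparison as it is.

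The cost is a few sentences in the SAP and a re-run on the same data in the same SPSS software, with no more participants or measurements.
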